5.2 SECONDARY ENDPOINTS

5.2.1 Key secondary endpoints

There are no key secondary endpoints defined for the trial.

5.2.2 Secondary endpoints

Overall survival

Overall survival (OS) will be calculated as the time from randomisation to death from any cause. Patients without evidence of death will be censored at the date of last contact when known to be alive.

Disease control

Disease control (DC), defined as a best overall response (BOR) of complete response (CR), partial response (PR), stable disease (SD) or Non-CR/Non-PD. SD and Non-CR/Non-PD must have been observed up until at least the Week 24 tumour assessment.

BOR is defined according to RECIST based on all evaluable tumour assessments from randomisation until the earliest of PD, start of subsequent anti-cancer therapy, loss to follow-up, withdrawal of consent or death. To be aligned with the primary endpoint derivation, tumour assessments after two or more consecutively missed assessments will not be considered.

Duration of disease control

Duration of DC will be calculated as the time from randomisation until the earliest of PD (according to RECIST) or death from any cause, among patients with DC.

The outcome rules defined in [Table 5.1: 1](#) will be used for the calculation.

Objective response

Objective response (OR), defined as a BOR (as detailed for DC) of CR or PR.

Time to pain progression or intensification of pain palliation

Time to pain progression or intensification of pain palliation, defined as the time from randomisation until the earliest of:

- ≥ 2 point increase from baseline in the Brief Pain Inventory – Short Form (BPI-SF), Item 3 (worst pain), without a decrease (of ≥ 1 point) from baseline analgesics use (via the 8-point Analgesic Quantification Algorithm [AQA]), or
- ≥ 2 point increase from baseline in the AQA, or
- Death

The rules to determine outcome (event or censored) along with the date of outcome are specified in [Table 5.2.2: 1](#). These rules will be applied to the independent assessment data prior to analysis.

[figure not shown]
In order to identify whether questionnaire assessments are missing, a nominal time-point based on the scheduling detailed in the CTP will be assigned to each assessment according to [Table 6.7: 2](#). If a patient does not have an assessment for both the BPI-SF, Item 3 and the AQA score at one of the scheduled time-points, it will count as a missed assessment;

[figure not shown]
otherwise, a response will be derived. If a ≥ 2 point increase from baseline in the BPI-SF, Item 3 is observed but the AQA score is missing, it will be assumed that no decrease in analgesics use has taken place.

[figure not shown]
Table 5.2.2: 1 Derivation rules for pain progression or intensification of pain palliation

[figure not shown]
Status at time of analysis	Outcome	Date of outcome
No baseline assessment and/or no post-baseline assessments		
Death on or before the second planned assessment	Event*	Date of death
Vital status is unknown or alive or death after second planned assessment	Censored	Date of randomisation
With baseline and at least one post-baseline assessment		
Alive and event-free, no more than one consecutively missed assessment	Censored*	Date of last assessment
Alive and event-free, two or more consecutively missed assessments	Censored*	Date of last assessment prior to missed assessments
Alive with event, no more than one consecutively missed assessment prior to event	Event*	Date of assessment of event
Alive with event, two or more consecutively missed assessments prior to event	Censored*	Date of last assessment prior to missed assessments
Death and event-free, no more than one consecutively missed assessment prior to death	Event*	Date of death
Death and event-free, two or more consecutively missed assessments prior to death	Censored*	Date of last assessment prior to missed assessments
Initiation of subsequent anti-cancer therapy		
Subsequent anti-cancer therapy started before outcomes flagged with a ‘*’ above	Censored	Date of last assessment before subsequent anti-cancer therapy (or date of randomisation if none exist)

[figure not shown]
* For these outcomes if initiation of subsequent anti-cancer therapy occurred prior to the outcome date then the rule for the final row of table will be used instead

[figure not shown]

[figure not shown]

[figure not shown]

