3.3.4.1 Withdrawal from trial treatment

An individual patient is to be withdrawn from trial treatment if:

- The patient wants to withdraw from trial treatment, without the need to justify the decision.
- The patient requires palliative radiotherapy or needs to take concomitant drugs that interfere with the investigational product or other trial medication (see [Section 4.2.2](#)).
- The patient can no longer be treated with trial medication for other medical reasons (such as surgery, adverse events, other diseases, secondary malignancy or pregnancy).
- Has radiologic documentation of progressive disease per RECIST version 1.1 ([Section 5.1](#)) unless the investigator documents that the patient, after discussion with the investigator, will continue treatment beyond progression due to clinical benefit ([Section 6.2.2.1](#)).
- The patient is diagnosed with ILD and meets the criteria for discontinuation in [section 4.4.3](#)
- The patient has repeatedly shown to be non-compliant with important trial procedures and, in the opinion of both, the investigator and sponsor representative, is not willing or able to stick to the trial requirements in the future.
- The patient violates eligibility criteria which would affect the safety of the patient (after discussion between the sponsor and the investigator).

- The patient entered the trial as premenopausal on ovarian suppression and estradiol increases above postmenopausal levels for more than 4 weeks (exceptions to this must be discussed with sponsor and patient may be able to stay treatment if they are clinically benefitting from treatment and reestablishment of ovarian suppression, e.g. by oophorectomy, is expected).

Given the patient's agreement, the patient will undergo the procedures for early treatment discontinuation (EOT and end of residual effect [EOR]/FU1 visit) and further follow up as outlined in the [Flow Chart](#) and [Section 6.2.3](#).

For all patients the reason for withdrawal from trial treatment (e.g. adverse events) must be recorded in the CRF. These data will be included in the trial database and reported.

Patients in whom visceral disease is detected by central review of baseline scan will have the possibility to continue treatment on trial after discussion of individual benefit/risk with their investigator.

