4.2.1.3 Concomitant treatments

Symptomatic treatments of tumour-associated symptoms are allowed. Concomitant medications or therapy to provide adequate supportive care may be given as clinically necessary.

After study enrolment, palliative radiotherapy is not allowed (see also [Section 3.3.4.1](#)).

See [Section 4.4.1.1](#) for recommendations on supportive treatments whilst on trial treatment.

Premenopausal women must be treated with concomitant ovarian suppression with GnRH agonists, e.g. goserelin acetate. Estradiol and FSH need to be in the postmenopausal range on ovarian suppression at the time of screening, and monitoring of estradiol to document that it remains in the postmenopausal range during trial treatment is mandatory. If the estradiol level increases above the postmenopausal range during treatment a repeat test should be performed within 4 weeks. If still outside of desired range see [Section 3.3.4.1](#).

Use of denosumab for symptomatic treatment of skeletal-related events in adults with bone metastases (see [Section 4.2.2.1](#)) and/or bisphosphonate therapy for the treatment of osteoporosis are permitted during the study according to guidelines and as per SmPC/PI. If bisphosphonate/denosumab therapy is initiated after enrolment, the reason for its use must be clearly documented in the CRF and progression of disease must be excluded.

All medications (other than study drugs), including anaesthetic agents, vitamins, homeopathic/herbal remedies, nutritional supplements starting from the date of signature of informed consent and ending at the EOR/FU1 visit must be listed on the concomitant medication page of CRF including trade name, start and end dates, indication for use etc. as specified in the [Flow Chart](#). Indicating “parenteral nutrition” or “anesthesia” without specifying details will be sufficient.

Hematopoietic growth factors should be reserved to cases of severe neutropenia and anemia as per the labelling of these agents following ASCO guidelines ([R16-1540](#)).

In case of major surgery no modifications for xentuzumab/placebo treatment are needed. For everolimus and exemestane please refer to current SmPC/PI

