5.6.2 Analgesics use

Pain palliation resulting from antitumor therapy provides direct evidence of treatment benefit when combined with evidence of antitumor activity ([R17-3501](#)). Intensification of pain palliation will be defined as a ≥ 2 -point increase in the 8-point Analgesic Quantification Algorithm (AQA, see [Table 5.6.2: 1](#)). AQA is a modification of the World Health Organization Analgesic Treatment Ladder that includes additional specificity for patients receiving strong opioids. This algorithm facilitates differentiation between the full ranges of doses of strong opioids used by patients and thus, more accurately enables researchers to determine and control for changes in levels of analgesic medication use over time in clinical trials ([R17-2771](#)). It will be completed by the investigator at the same visits as the PROs.

Table 5.6.2: 1 AQA

AQA score	Description
0	No analgesic
1	Non-opioid analgesics
2	Weak opioids
3	Strong opioids ≤75 mg OME per day
4	Strong opioids >75–150 mg OME per day
5	Strong opioids >150–300 mg OME per day
6	Strong opioids >300–600 mg OME per day
7	Strong opioids >600 mg OME per day

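### Radiotherapy given for tumour pain is not an event in the time-to-pain endpoint, so a patient irradiated before a questionnaire records worsening is censored or carried as event-free

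*SAP*

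**What the plan says.** **The endpoint.** SAP 5.2.2 words it as "Time to pain progression or intensification of pain palliation, defined as the time from randomisation until the earliest of" three events. The first is a rise of at least 2 points in BPI-SF Item 3 (worst pain) "without a decrease (of ≥ 1 point) from baseline analgesics use". The second is "≥ 2 point increase from baseline in the AQA, or" and the third is death. Protocol 5.6.2 fixes the palliation limb: "Intensification of pain palliation will be defined as a ≥ 2 -point increase in the 8-point Analgesic Quantification Algorithm". Every level of the AQA table there, 0 to 7, is a class or dose of analgesic drug. Protocol 2.1.3 and 7.3.2 use the same three components.

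**Radiotherapy.** Protocol 3.3.4.1 lists among the reasons for stopping trial treatment: "The patient requires palliative radiotherapy or needs to take concomitant drugs that interfere with the investigational product or other trial medication". Protocol 4.2.1.3 adds: "After study enrolment, palliative radiotherapy is not allowed". Exclusion criterion 9 (Protocol 3.3.3) shows that the protocol regards radiotherapy as a treatment for pain, because it has a separate rule for local radiotherapy given as analgesia before the study.

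**Censoring.** The last row of SAP Table 5.2.2: 1, "Subsequent anti-cancer therapy started before outcomes flagged", censors the patient at the last assessment before that therapy. The footnote makes this row override any event dated later.

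**The concern.** Many of these patients have bone disease, where radiotherapy is one way of treating pain that drugs do not control. Under this plan, a patient who goes to radiotherapy before her worsening is captured on a questionnaire has had her palliation intensified and has had to leave trial treatment, yet the endpoint records no failure. Whether she is censored or stays at risk with the pain treated, the reason is closely tied to the outcome being measured. The censoring is then informative, pain failure is understated, and the comparison between arms depends on how often failure takes this form in each arm.

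**Working it through.** The documents give no event count, power or radiotherapy rate for this endpoint, so there is no plan figure to reproduce. The check is a reading of the rules, followed by an illustration on assumed shares.

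**Step 1: who is affected.** Questionnaires are due on day 1 of each cycle (every 28 days to cycle 20, every 56 days after), at end of treatment (EOT), at the first follow-up visit, and during follow-up for progression (Protocol Flow Chart; SAP 6.7). AQA is completed at the same visits (Protocol 5.6.2).

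- Threshold crossed at an assessment before radiotherapy starts, including an EOT visit held first: already an event.
- Radiotherapy starts before any assessment records a crossing: not an event at that point. Item 3 asks only about the previous 24 hours, so worsening between visits can be missed.

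**Step 2: how the second group is scored.**

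| If radiotherapy is | Result under Table 5.2.2: 1 |
|---|---|
| subsequent anti-cancer therapy | Censored at the last prior assessment; a crossing at a later EOT visit is overridden. Follow-up for progression ends when further anti-cancer treatment starts, and survival follow-up has no questionnaires |
| not subsequent anti-cancer therapy | Stays at risk; later questionnaires score the relieved pain. A later rise or death still counts |

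Protocol 4.2.2.1 lists radiotherapy alongside prohibited anti-cancer treatments. Protocol 6.2.3.1 describes what is recorded as subsequent therapy in terms of a drug and/or best supportive care. Neither settles the class.

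**Step 3: illustration, censoring route.** Let *s* be the share of all first composite events, deaths included, that appear first as radiotherapy (C = control, X = xentuzumab). With exponential times:

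- observed HR = true HR × (1 − sX)/(1 − sC)
- events kept = 1 − s; Kaplan-Meier median overstated by 1/(1 − s)

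Equal shares, HR unchanged:

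| s | Events lost | Median factor |
|---|---|---|
| 5% | 5% | 1/0.95 = 1.05 |
| 10% | 10% | 1/0.90 = 1.11 |
| 20% | 20% | 1/0.80 = 1.25 |
| 30% | 30% | 1/0.70 = 1.43 |

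Unequal shares:

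| True HR | sC | sX | Observed HR |
|---|---|---|---|
| 0.60 | 20% | 10% | 0.60 × 0.90/0.80 = 0.675 |
| 0.60 | 10% | 20% | 0.60 × 0.80/0.90 = 0.533 |
| 1.00 | 20% | 10% | 1.00 × 0.90/0.80 = 1.125 |
| 1.00 | 10% | 20% | 1.00 × 0.80/0.90 = 0.889 |

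Because *s* is a share of all first events, deaths dilute it. If *f* is the share among pain failures only and *d* the share of first events that are deaths, then s = f × (1 − d), which is smaller than *f*. Putting *f* straight into the formula would overstate the effect.

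**Step 4: illustration, stays-at-risk route.** This needs an assumption about what follows radiotherapy. A simulation with 200,000 patients per arm used exponential times, a control median of 9.9 months (borrowed from the PFS assumption in Protocol 7.7 for scale only), follow-up of 30 − 15/2 = 22.5 months, and an unchanged event rate after radiotherapy. With shares of 20% (control) and 10% (xentuzumab), a true HR of 0.60 reads about 0.66 and a true HR of 1.00 about 1.11. With 20% in both arms the HR stays at 0.60, but the control proportion with an event falls from 79.3% to 72.7%.

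**The case against.** The best defence is that the definition is deliberate. Protocol 2.1.3, 5.6.2 and 7.3.2 agree with the SAP that palliation means AQA, so counting radiotherapy changes a protocol endpoint. Radiotherapy is not the same as pain failure either: exclusion criterion 9 also names lytic lesions at risk of fracture. Questionnaires are frequent, and the need for radiotherapy triggers withdrawal and therefore an EOT questionnaire. Prohibited treatment is already tabulated as important deviation D1 (SAP 6.2). The SAP covers only the non-expanded trial, read exploratively (SAP 3), with no key secondary endpoints (SAP 5.2.1).

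Much of this stands, and it rules out three stronger readings.

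- A reader might infer that every irradiated patient is mis-scored. Those with a recorded crossing beforehand are not.
- A reader might infer bias toward no effect, on the argument that xentuzumab protects bone and so makes radiotherapy rarer. The formula depends on the share of failures that appear first as radiotherapy, not on its rate. If xentuzumab cut every kind of pain failure equally, radiotherapy would be rarer but sX = sC, and the HR would not move.
- A reader might take the AQA-only definition as an internal contradiction. It is consistent throughout; what is missing is a rule for radiotherapy.

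The objection does not close the gap. EOT may fall up to 14 days after stopping and so after radiotherapy has begun, and a deviation table does not alter the derived outcome.

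**Conclusion.** The point holds in limited form. Radiotherapy for tumour pain that starts before an assessment records a threshold crossing is not counted as a failure, and its handling is both outcome-related and unspecified. Pain failure is understated on either route.

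The size cannot be stated. The figures above rest on assumed shares of 5% to 30% and exponential times, and the stays-at-risk figures also on an assumed course after radiotherapy. They show how the rules behave and do not estimate this trial's bias. With equal shares the loss falls on events and event-free times only; with unequal shares the HR can move in either direction.

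The endpoint is secondary and exploratory. Neither primary PFS nor the PFS-based expansion criterion is affected. Parts of the SAP are redacted, but this endpoint's definition and derivation table can be read, and no visible rule covers radiotherapy.

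**What to change.** 1. In SAP Table 5.2.2: 1, state whether radiotherapy given for tumour pain counts as subsequent anti-cancer therapy in the protocol-defined, AQA-only analysis.
2. Pre-specify a second analysis in which the start of palliative radiotherapy recorded for tumour pain is an event on its start date and is not treated as subsequent anti-cancer therapy for this endpoint. Report it beside the AQA-only result.
3. Because the protocol fixes the AQA-based definition, list this in SAP section 4 as a declared change, or run it as a sensitivity analysis. Protocol 1.4 already reports the primary PFS analysis as complete; if the pain endpoint has also been analysed, label the addition post hoc.

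The cost is mainly wording and derivation. The reason for stopping treatment is in the CRF (Protocol 3.3.4.1), and concomitant therapies are recorded to the first follow-up visit (Protocol 6.2.1). Two limits should be stated with the result. The indication, pain or fracture risk, has to be read from the CRF entry, and the documents do not confirm that it is always there. After the first follow-up visit, radiotherapy may be incompletely recorded, since Flow Chart note 20 then restricts concomitant medication to treatment of drug-related SAEs and AESIs.

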6. GENERAL ANALYSIS DEFINITIONS

6.1 TREATMENTS

For reporting purposes, all randomised patients will be classified into either 'Xe1000+Ev10+Ex25' or 'Plc+Ev10+Ex25' as randomised. For efficacy analyses, the intent-to-treat (ITT) approach will be used, i.e. patients will be analysed according to the treatment group they were randomised to. All planned analyses will be presented by this randomised treatment group. Handling of patients where treatment group assignment has not been followed will be handled on a case-by-case basis, to be agreed at report planning meetings prior to database lock. The following study periods are defined:

- Screening: day of informed consent to day prior to first administration of study treatment
- Treatment: day of first administration of study treatment to day of last administration of study treatment
- Residual effect period (REP): day after last administration of study treatment, for a duration of 42 days
- Follow-up: day after the end of the REP to trial completion

For safety analyses, treated patients will be analysed according to the initial treatment taken, and for safety summaries, data recorded whilst taking study treatment and up to 42 days after last administration of study treatment (i.e. including the REP) will be considered as on-treatment. As the treatment arms are made up of a combination of individual treatments, a patient may have multiple last doses of treatment; therefore, the last dose of study medication is defined as the latest of these.

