The primary efficacy analyses will be performed on the randomised set (RS), consisting of all randomised patients. Patients randomised and not treated will be analysed according to the censoring rules defined in [Section 7.5](#). Randomised patients who receive the wrong treatment will be analysed according to their planned randomised treatment group. No per-protocol analysis is planned.

Stratification (where stated) of analyses will be based on the presence of baseline bone-only metastases (Yes/No), prior CDK4/6 inhibitor treatment (Yes/No) and menopause status (pre/post). Refer to [Section 7.6](#) for further details on the randomisation stratification factors.

The safety analysis will be based on the treated set (TS), consisting of all patients treated with at least one dose of any study treatment. Patients will be analysed according to the actual treatment received.

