7.3.4 Safety analyses

Adverse events will be coded using the Medical Dictionary for Drug Regulatory Activities (MedDRA). Standard BI summary tables and listings will be produced. All adverse events with an onset between start of treatment and end of the REP, a period of 42 days after the last dose of trial medication, will be assigned to the on-treatment period for evaluation. As the treatment arms are made up of a combination of individual treatments a patient may have multiple last doses of treatment; therefore the last dose of study medication is defined as the latest of these.

All treated patients will be included in the safety analysis, according to the actual trial medication they received. In general, safety analyses will be descriptive in nature and will be based on BI standards. No hypothesis testing is planned.

Statistical analysis and reporting of adverse events will concentrate on treatment-emergent adverse events, i.e. all adverse events occurring between start of treatment and end of the residual effect period. Adverse events that start before first drug intake and deteriorate under treatment will also be considered as ‘treatment-emergent’.

Frequency, severity, and causal relationship of adverse events will be tabulated by system organ class and preferred term after coding according to the current version of the MedDRA at the database lock.

Laboratory data will be analysed both quantitatively as well as qualitatively. The latter will be done via comparison of laboratory data to their reference ranges. Values outside the reference range as well as values defined as clinically relevant will be summarised. Treatment groups will be compared descriptively with regard to distribution parameters as well as with regard to frequency and percentage of patients with abnormal values or clinically relevant abnormal values.

Vital signs, physical examinations, or other safety-relevant data observed at screening, baseline, during the course of the trial and at the end-of-trial evaluation will be assessed with regard to possible changes compared to findings before start of treatment.

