6.2 IMPORTANT PROTOCOL DEVIATIONS

No per protocol set (PPS) analysis will be performed, hence, no patient will be excluded from the analyses (with the exception of patients not providing informed consent). However, patients with potentially important protocol deviations (iPDs) will be documented to give an indication of the level of adherence to the protocol, refer to [Table 6.2: 1](#). Note this is a working list and may not be finalised until the final Medical Quality Review Meeting (MQRM), Database Lock Meeting (DBLM) and Report Planning Meeting (RPM) have taken place prior to the database lock of the primary PFS analysis.

A frequency table of the above iPDs will be produced. In addition, a frequency table of all COVID-19 related non-important and important PDs will be produced.

Table 6.2: 1 Handling of iPDs

[figure not shown]
iPD code	iPD Category & Brief Description	Analysis Set Excluded from
A1	Diagnosis of trial disease questionable	None
A2	Prohibited baseline condition, diagnosis or treatment	None
A3	Laboratory result indicating inadequate organ function at screening	None
A4	Adequate archival tumour tissue not available	None
B1	Informed consent not available/not done	All
B2	Informed consent too late	None
B3	Age limit for patient inclusion not adhered to	None
C1	Time window violation for procedures performed at screening	None
C2	Trial medication not given according to protocol	None
C3	Infusion time for the investigational treatment outside of CTP specific boundaries	None
C4	Randomisation not followed	None
D1	Prohibited treatment during trial conduct phase	None
E1	Imaging assessments not done according to CTP instructions	None
F1	Other protocol violations affecting patient rights or safety	None

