7.8.1 Adverse Events

AEs will be coded with the most recent version of the MedDRA. The severity of AEs will be scaled according to Common Terminology Criteria (CTC) AE version 5.

Unless otherwise specified, the analyses of AEs will be descriptive in nature. All analyses of AEs will be based on the number of patients with AEs and not on the number of AEs.

For analysis, multiple AE occurrence data on the eCRF will be collapsed into an AE if all of the following applies:

- All AE attributes are identical (Lowest Level Term [LLT], CTCAE grade, action taken with trial medication, therapy required, seriousness, reason for seriousness, relationship, outcome, AE of special interest)
- The occurrences are time overlapping or time-adjacent (time-adjacency of 2 occurrences is given if the second occurrence started on the same day or on the day after the end of the first occurrence).

For further details on the analysis and presentation of AE data refer to BI standards [\(5\)](#).

The analysis of AEs will be based on the concept of treatment emergent adverse events. That means that all AEs with an onset between first drug intake and last drug intake + REP (42 days) will be assigned to the randomised treatment. All AEs with an onset before first drug intake will be assigned to 'screening' and all AEs with an onset after the residual effect period will be assigned to 'post-treatment' (for listings only). For details on the treatment definition, see [Section 6.1](#).

An overall summary of AEs will be presented; along with the standard categories presented additional categories for action taken and drug relationship with each compound, worst CTCAE grade and infusion related reaction response. The frequency of patients with AEs will be summarised by treatment, highest CTCAE grade, primary SOC and PT. The SOC's will be sorted alphabetically; PT's will be sorted by decreasing frequency (within SOC). Only AEs with a given CTCAE grade will be displayed in tables showing AEs by worst CTCAE grade. AEs with a missing CTCAE grade will not be displayed in these tables; a footnote will explain that these AEs are not included and a separate listing of them will be produced if required. The following tables will be produced for AEs during the on-treatment period:

- Patients with AEs
- Patients with any related AE

- Patients with related xentuzumab/placebo AEs
- Patients with related everolimus AEs
- Patients with related exemestane AEs
- Patients with SAEs

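### The protocol and SAP give three different rules for the arm under which a patient's safety data are reported, and no rule is named as the default

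*SAP*

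**What the plan says.** **Protocol.** Section 7.3 defines the treated set for safety and adds: "Patients will be analysed according to the actual treatment received". Section 7.3.4 repeats the rule: "All treated patients will be included in the safety analysis, according to the actual trial medication they received".

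**SAP 6.1.** After describing the intention-to-treat approach for efficacy, the section states: "All planned analyses will be presented by this randomised treatment group". Patients whose assignment was not followed "will be handled on a case-by-case basis, to be agreed at report planning meetings prior to database lock". Further down, for safety, "treated patients will be analysed according to the initial treatment taken".

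**SAP 7.8.1.** Adverse events starting between first drug intake and 42 days after the last "will be assigned to the randomised treatment". The paragraph closes with "For details on the treatment definition, see" and a pointer to Section 6.1.

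**SAP Section 3** says the SAP is based on Section 7 of the protocol. **SAP Section 4**, which lists changes from the protocol's methods, contains only the COVID-19 item.

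**SAP Table 6.2: 1** includes deviation code C4, "Randomisation not followed". It removes the patient from no analysis set.

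**The concern.** Each of the three texts is a stated rule, so this is a contradiction and not a gap. Two programmers working from the two documents could place the same patient in different arms, and each could cite a sentence in support.

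The SAP foresees the patients concerned through code C4 and keeps them in the safety tables, so each of them needs an arm. What is at stake is whether the adverse event tables describe people exposed to the drug named at the head of the column, and whether that placement was fixed before anyone knew the results.

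**Working it through.** The plan states no figure on this point, so there is none to reproduce. The check sets the rules side by side and then sizes the effect under stated assumptions.

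**Step 1. Apply each rule to each kind of patient.**

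| Patient | Protocol 7.3, 7.3.4 (actual) | SAP 6.1, safety sentence (initial) | SAP 6.1 general sentence and 7.8.1 (randomised) |
|---|---|---|---|
| Treated as randomised | same arm | same arm | same arm |
| Randomised to placebo, xentuzumab throughout | xentuzumab | xentuzumab | placebo |
| Randomised to xentuzumab, placebo throughout | placebo | placebo | xentuzumab |
| Randomised to and started on placebo, later given xentuzumab in error | not defined: received both | placebo | placebo |
| Randomised to placebo, first infusion xentuzumab in error, then placebo | not defined: received both | xentuzumab | placebo |

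Rows 2 and 3 are a direct conflict between the protocol and SAP 7.8.1, and also between SAP 7.8.1 and the safety sentence of SAP 6.1. Rows 4 and 5 show that the protocol's rule is itself incomplete for mixed exposure.

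**Step 2. Follow the cross-reference.** SAP 7.8.1 sends the reader to SAP 6.1 for the treatment definition. SAP 6.1 holds both the randomised-group sentence and the initial-treatment sentence, so the reference does not settle which applies.

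**Step 3. Size.** Inputs: about 40 patients per arm (Protocol synopsis). The event counts are assumed, because the documents give none: 12 xentuzumab and 4 placebo patients with the event among patients other than the mis-treated ones. Let k placebo-randomised patients receive xentuzumab throughout, all with the event.

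- As randomised: difference = 12/40 − (4 + k)/40
- As actual: difference = (12 + k)/(40 + k) − 4/(40 − k)

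| k | As randomised | As actual | Shift |
|---|---|---|---|
| 0 | 20.0 points | 20.0 points | 0 |
| 1 | 17.5 | 13/41 − 4/39 = 21.5 | +4.0 |
| 2 | 15.0 | 14/42 − 4/38 = 22.8 | +7.8 |
| 3 | 12.5 | 15/43 − 4/37 = 24.1 | +11.6 |

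With a rarer event (4 and 0 other patients) the shifts for k = 1, 2, 3 are 4.7, 9.3 and 13.8 points.

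**Step 4. Two variations on the 12 and 4 case.**

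- *Error in the other direction.* One xentuzumab-randomised patient receives placebo throughout and has the event. As randomised: 13/40 − 4/40 = 22.5 points. As actual: 12/39 − 5/41 = 30.8% − 12.2% = 18.6 points. The shift is −3.9.
- *No event in the mis-treated patient.* One placebo-randomised patient receives xentuzumab and has no event. As randomised: 12/40 − 4/40 = 20.0. As actual: 12/41 − 4/39 = 29.3% − 10.3% = 19.0. The shift is −1.0.

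**The case against.** The best defence reads the SAP more kindly. The randomised-group sentence in SAP 6.1 follows straight after the efficacy sentence and may be meant only for efficacy, which would leave the safety sentence to govern safety. SAP 7.8.1 is sorting events by time, so randomised treatment there may simply label the on-treatment window. Initial treatment may be the SAP's way of making actual treatment workable: the two agree for anyone given the wrong arm throughout, and where they could differ, the protocol is silent. Finally, the case-by-case provision covers exactly these patients, and codes C2 and C4 would show them in a frequency table.

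Much of this has weight, and it keeps the point small. It does not remove the contradiction. The SAP states none of these readings. The randomised-group sentence is worded to cover every planned analysis. Taken as written, SAP 7.8.1 places a patient given the wrong arm from the first dose differently from the protocol. The case-by-case provision gives no default and no criterion.

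A reader might also infer that the plan tends to hide xentuzumab toxicity in the placebo arm. The documents do not support that. Misplacement can run either way, as Step 4 shows. Nor do they suggest that mis-dosing is likely: assignment of xentuzumab or placebo is managed through IRT (Protocol 4.1.5), and an unblinded monitor checks compliance in the pharmacy (Protocol 4.1.6.1). It is also tempting to say that each misplaced patient moves an arm's rate by 1/40 = 2.5 points. That requires the patient to have the event and ignores the change in both denominators.

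**Conclusion.** The inconsistency is real: three rules for one decision, and no declared departure from the protocol. Its reach is narrow. It touches only patients not treated as randomised, whose number the documents do not give, and it has no effect if there are none. For those given the other arm's infusions throughout, SAP 7.8.1 read literally reports events under an arm whose drug they did not receive.

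The Step 3 shift of about 4 to 5 points in the between-arm difference for one such patient is an illustration. It rests on 40 per arm, the assumed event counts, and the patient having the event. Protocol 7.3.4 makes safety analysis descriptive without hypothesis testing, so no error rate is involved. This is a minor correction, worth making because it is cheap and the tables would otherwise depend on an unstated choice.

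**What to change.** 1. In SAP 6.1, limit the randomised-group sentence to efficacy analyses.
2. In the safety sentence of SAP 6.1 and in SAP 7.8.1, replace the initial-treatment and randomised-treatment wording with the protocol's rule: actual treatment received.
3. State, before unblinding, one convention for patients who received both xentuzumab and placebo infusions. One option is to keep initial treatment taken explicitly for that case only and list those patients separately. Placing anyone with at least one xentuzumab infusion in the xentuzumab group is another possible convention, but it is in neither document. It would also count events that occurred before the stray infusion under xentuzumab.
4. List any intended departure from Protocol 7.3 in SAP Section 4.

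The cost is a few sentences of SAP text, with no new data and no change to the sample size. Protocol 1.4 reports that the primary analysis is complete. If the safety tables were produced under the present wording, the trial report should say which rule was used and how many patients it affected.
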